 14.3.2 Efficacy Analyses48

15 Patient Consent and Peer Judgement.....49

16 References50

List of Tables

Table	Page
Table 2.1 Schedule of Activities.....	11
Table 3.1 Summary of Phase I DLTs.....	20
Table 3.2 Summary of Related TEAEs in >10% of the patients (total)	21
Table 4.1 Objectives	21
Table 8.1 Management Recommendations for Skin Reactions	31

List of Appendices

Appendix		Page
Appendix 1	Abbreviations and Definitions	55
Appendix 2	Study Governance, Regulatory, and Ethical Considerations	58
Appendix 3	Creatinine Clearance Formula	60
Appendix 4	Dose Modification of LY3214996 & Abemaciclib	61
Appendix 5	Sensitive CYP3A Substrates and Narrow Therapeutic Range Drugs.....	66
Appendix 6	Patient Dosing Instructions and Diary	67

1 Synopsis

TITLE	A Phase 2 basket trial of an ERK1/2 inhibitor (LY3214996) in combination with abemaciclib for patients whose tumors harbor pathogenic alterations in BRAF, RAF1, MEK1/2, ERK1/2, and NF1.
PHASE	2
OBJECTIVES	
Primary Objective:
 
 To evaluate the proportion of patients with objective response to an ERK1/2 inhibitor (LY3214996) in combination with abemaciclib for patients whose tumors harbor pathogenic alterations in BRAF, RAF1, MEK1/2, ERK1/2, and NF1 
Secondary Objective:
 
 To evaluate the safety and tolerability of LY3214996 + abemaciclib as defined by CTCAE v5 criteria. To evaluate the median progression-free survival (PFS). To evaluate the duration of response (DOR). 
Correlative Objectives:
 
 To identify potential predictive biomarkers beyond the genomic alteration by which treatment is assigned and/or resistance mechanisms. To evaluate pharmacokinetic parameters of LY3214996 and abemaciclib.
STUDY DESIGN	Single arm, non-randomized, open-label
TOTAL NUMBER OF SUBJECTS	35
KEY INCLUSION CRITERIA	
 1. Patients must have histologically confirmed, metastatic/advanced cancer with tumors that harbor the following alterations as defined below using a CLIA-certified next-generation sequencing: 
 a. Point mutations in BRAF, RAF1, MEK1/2, or ERK1/2 that have been previously characterized to be gain-of-function mutations. These mutations have to be specified as gain-of-function as listed in the OncoKB and/or JAX-CKB databases. 
 i. Patients with NSCLC that harbor BRAF V600E treated with prior RAF and/or MEK inhibition therapy will be excluded ii. Patients with tumor types other than NSCLC that harbor BRAF V600E mutations who have been treated and progressed on prior BRAF and/or MEK inhibition will be included iii. Patients with NSCLC that harbor BRAF V600E will only be enrolled if they are not a candidate for FDA approved therapy b. Amplification of RAF1 defined as > 6 copies of the respective gene. c. Gene fusions in which BRAF, RAF1, MEK1/2 or ERK1/2 is a fusion partner; in which the fusion is determined to be in-frame; and the kinase domain of BRAF, RAF1, MEK1/2, or ERK1/2 is retained. d. Point mutations, frameshift insertions/deletions, splice site mutations, or stop gain mutations that results in loss-of-function of NF1.

	
 2. Measurable, metastatic disease amenable to biopsy. If biopsy is deemed unsafe at time of procedure, patients will remain eligible for study. 3. ECOG performance status 0 or 1. 4. Laboratory evidence of adequate organ function and hematologic function. 5. Patients with untreated brain metastases are excluded. However, patients with metastatic CNS tumors may participate in this trial, if the patient is > 4 weeks from therapy completion (incl. radiation and/or surgery), is clinically stable at the time of study entry and is receiving a stable or decreasing dose of corticosteroid therapy. Brain MRI or head CT is required at screening for patients with known brain metastases. 6. Patients who have received prior treatment with an ERK kinase inhibitor are excluded
TREATMENT PLAN	Abemaciclib 150 mg orally twice daily with LY3214996 200 mg orally daily until disease progression, unacceptable toxicity, or patient preference to withdraw from study.
STATISTICAL CONSIDERATIONS	
The primary end point is overall response rate (ORR), where overall response is defined as the complete or partial response per RECIST v1.1 criteria. We will use the one stage design for the phase II trial. We will specify the null hypothesis that the true ORR is 5% versus the alternative hypothesis that that the true ORR is 19% using a one-sided test with the designing parameters type-I error=0.05 and type II error=0.2 (power=80%).
 
A total sample size of 28 evaluable patients will be accrued. Of note, an evaluable patient is defined as a patient who receives at least one dose of trial drug. Assuming a 20% drop-out rate, it is anticipated that the total accrual would be 35 patients.
 
An additional early stopping rule for futility will be used to monitor the following subgroups of patients with pathogenic alterations in 1) BRAFV600E 2) BRAF nonV600E, RAF1 3) MEK1/2, ERK1/2 and 4) NF1 based on the Bayesian posterior probability.

ESTIMATED ENROLLMENT PERIOD	12 months
ESTIMATED STUDY DURATION	18 months

2 Schedule of Activities

Table 2.1 presents the schedule of activities for patients receiving LY3214996 in combination with abemaciclib.

Table 2.1 Schedule of Activities

Study Evaluation Cycle = 28 days	Screening	Cycle 1		Cycle 2		Cycle 3 and beyond	Safety follow up visit
	-21 ± 7 days	Day 1	Day 15 ± 3 days	Day 1 ± 3 days	Day 15 ± 3 days	Day 1 ± 7 days	30 days (±7) post last dose
REQUIRED ASSESSMENTS							
Informed Consent	X						
Demographics	X						
Medical History ^A	X						
Concomitant Medications	X	X		X		X	X
Physical Exam	X	X	X	X	X	X	X
Vital signs and ECOG Performance Status	X	X	X	X	X	X	X
Height	X						
Weight	X	X	X	X	X	X	X
Adverse Event Evaluation ^B	X	X	X	X	X	X	X
LABORATORY ASSESSMENTS							
Complete Blood Cell Count with differential (CBC) ^J	X	X	X	X	X	X	X
Comprehensive Metabolic Profile (CMP) ^C	X	X	X	X	X	X	X
Pregnancy test (serum or urine) (WOCBP) ^D	X	X		X		X	X
DISEASE ASSESSMENT							
CT of chest ^E	X					X	
CT or MRI of abdomen and pelvis ^E	X					X	
TREATMENT EXPOSURE							

Study Evaluation Cycle = 28 days	Screening	Cycle 1		Cycle 2		Cycle 3 and beyond	Safety follow up visit
	-21 ± 7 days	Day 1	Day 15 ± 3 days	Day 1 ± 3 days	Day 15 ± 3 days	Day 1 ± 7 days	30 days (±7) post last dose
LY3214996 and abemaciclib ^F		X	X	X	X	X	
SPECIMEN COLLECTION							
Tissue biopsies at screening and at progression ^G	X						X
Blood sample for plasma ctDNA		X		X		X	X
Blood for germline mutations	X						
Pharmacokinetics (PK) ^H			X	X			

A: Medical history to include prior treatments, radiation and surgical history. Diagnosis and staging to include pathology report and Tumor Node Metastasis (TNM) staging 8th edition.
 
B: CTCAE Version [5.0] Adverse Events will be collected from the time informed consent is signed through 30 days after the last dose of study treatment.
 
C: To include albumin, alkaline phosphatase, ALT, AST, bicarbonate, BUN, calcium, chloride, creatinine, glucose, lactate dehydrogenase, magnesium, phosphorus, potassium, sodium, total bilirubin, and total protein.
 
D: All females of childbearing potential must have a negative blood or urine pregnancy test within 14 days prior to enrollment and prior to treatment on day 1
 
E: CT or MRI scans of chest and abdomen will be done at baseline to assess the response per RECIST v1.1 criteria. CTs or MRIs of the abdomen with IV contrast are encouraged but will be done at the investigator's discretion. Disease assessments should be completed every odd cycle (i.e. cycle 3, cycle 5, etc.).
 
F: Antiemetic prophylaxis will be required in cycle 1 in an effort to improve patient safety and reduce the incidence of nausea and vomiting. Refer to Section 8.6.1.3 for details.
 
G: Biopsy at screening is mandatory if deemed safe by the treating physician and should be completed following determination of eligibility, ≤14 (+/- 7) days before start of treatment. Patients unable to undergo the screening biopsy may donate archived tissue if available. See Section 10.5.2 for details. Biopsy at time of progression is not mandatory.
 
H: Plasma samples for pharmacokinetics will be collected on cycle 1 day 15 and cycle 2 day 1 prior to dosing of abemaciclib and LY3214996. Please refer to Section 10.3.
 
I: Vital signs to be performed per standard of care and should include heart rate, blood pressure, respiratory and oxygen saturation
 
J: To include WBC, ANC, platelets, and Hgb
							

3 Introduction

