8.1.3 Selection and Timing of Doses

A cycle is defined as an interval of 28 days. A delay of a cycle due to holiday, weekend, bad weather, or other unforeseen circumstances will be permitted for a maximum of 7 days and not counted as a protocol deviation. The reason for the treatment interruption should be documented

on the CRF. A cycle begins when study treatment is dispensed for the cycle and administered. Thus, if an expected cycle start is delayed, the number of days in the current cycle is increased beyond 28 days.

A patient may continue to receive study treatment until confirmed progressive disease (Section 10.1), unacceptable toxicity, or discontinuation for any other reason (Section 9).

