8.3 Dosage Modification

Please refer to [Appendix 4](#) for dose adjustment guidelines.

Study therapy may be held up to 3 weeks to allow sufficient time for recovery. Patients who do not recover from drug-related toxicity to \leq grade 1 within 3 weeks will be discontinued (except alopecia, fatigue, skin rash, elevated creatinine, nausea, vomiting, constipation or diarrhea that can be controlled with treatment). If a dose adjustment is made, the patient must be maintained at the reduced dose level for all remaining cycles.

For the purposes of dose modification, the investigator must first assess if the toxicity is considered at least possibly due to one of the study drugs, and must then apply the study drug-specific dose-modification guidelines accordingly. If the toxicity is not clearly attributable to either individual study drug, then the causality should be attributed to both study drugs. Dosing interruptions of any study drug are permitted for reasons not related to study treatment (for example, minor surgery, unrelated medical events, patient vacation, and/or holidays). The reason for interruption should be documented on the CRF.

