10.1 Efficacy Assessments

Tumor assessments will be performed for each patient at the times shown in the Schedule of Activities ([Section 2](#)).

Computed tomography (CT) scans, including spiral CT, are the preferred methods of measurement (CT scan thickness recommended to be ≤ 5 mm); however, magnetic resonance imaging (MRI) is also acceptable in certain situations, such as when body scans are indicated or if there is a concern about radiation exposure associated with CT. Intravenous and oral contrast is required unless medically contraindicated.

The CT portion of a positron emission tomography (PET)-CT scan may be used as a method of response assessment if the site can document that the CT is of identical diagnostic quality to a diagnostic CT (with intravenous and oral contrast). A PET scan alone or as part of a PET-CT may be performed for additional analyses but cannot be used to assess response according to RECIST v.1.1 (Eisenhauer et al. 2009).

The method of tumor assessment used at baseline must be used consistently throughout the study. Each patient's full extent of disease will be assessed using RECIST v1.1 (Eisenhauer et al. 2009).

See Section 14.3.2 for definitions of the efficacy endpoints.

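### Scans follow cycle number, not time from first dose, so a delayed cycle start postpones later tumor assessments and makes PFS and DOR partly depend on dose delay

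*Combined protocol and SAP*

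**What the plan says.** - **Scan schedule.** Section 2, Table 2.1, footnote E: "Disease assessments should be completed every odd cycle (i.e. cycle 3, cycle 5, etc". The imaging rows sit in the column for cycle 3 and beyond, whose ±7-day window is attached to Day 1 of the cycle.
- **No separate imaging calendar.** Section 10.1: "Tumor assessments will be performed for each patient at the times shown in the Schedule of Activities".
- **Cycle definition.** Section 8.1.3: "A cycle is defined as an interval of 28 days", and "A cycle begins when study treatment is dispensed for the cycle and administered".
- **Effect of a delay.** Section 8.1.3: "Thus, if an expected cycle start is delayed, the number of days in the current cycle is increased beyond 28 days". The same paragraph deals with delays for holidays, weather and similar reasons, which are "permitted for a maximum of 7 days and not counted as a protocol deviation".
- **Toxicity holds.** Section 8.3: "Study therapy may be held up to 3 weeks to allow sufficient time for recovery". Appendix 4 holds both drugs for Grade 2 or higher nausea, vomiting or diarrhea, but holds abemaciclib alone for hematologic toxicity. It also permits doses to be omitted within a cycle.
- **Endpoints.** Section 14.3.2.1 dates PFS at the first observed clinical or radiologic progression or death, and ends DOR at objectively documented progression. Section 14.3.2.2.2 analyses both by Kaplan–Meier, with no rule for late assessments.

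**The concern.** Progression on imaging can be dated only on the day of a scan. If the scan day moves with dosing, a patient whose cycle start slips is imaged later than one whose cycles run on time, for a reason connected with tolerability rather than tumor growth. The interval between scans then differs between patients, and the recorded PFS and DOR carry a component that reflects dose delay.

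Median PFS is a stated secondary objective. In a single-arm trial it can be read only against outside data, where the timing of assessments matters. The ±7-day window does not help, because it moves with the cycle.

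**Working it through.** **1. The plan's own figures.** The only design calculation concerns ORR (Section 14.1). With 28 patients and success at 4 or more responses, the exact binomial gives P(X ≥ 4 | 5%) = 0.0491 and P(X ≥ 4 | 19%) = 0.8065, and 28/(1 − 0.20) = 35. These reproduce. They depend on best response and not on when a scan occurs, so scan timing does not alter them. The documents give no target or precision for PFS or DOR.

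**2. Scan days.** Nominal cycle 3 day 1 = 2 × 28 + 1 = day 57, and cycle 5 day 1 = 4 × 28 + 1 = day 113. If one cycle start before cycle 3 is delayed by h days, both move by h:

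| Delay of the cycle start | First scan | Second scan |
|---|---|---|
| 0 days | 57 | 113 |
| 7 days | 64 | 120 |
| 14 days | 71 | 127 |
| 21 days | 78 | 134 |

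What counts is the delay of the cycle start, not the length of the hold. A 21-day hold beginning two weeks before the next cycle is due delays that start by about 21 − 14 = 7 days.

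**3. Direction for one patient.** Take a 14-day delay (scans on days 71 and 127 instead of 57 and 113).

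- Progression on day 40 is dated day 71 instead of 57: 14 days later.
- Progression on day 100 is dated day 127 instead of 113: 14 days later.
- Progression on day 65 is dated day 71 instead of 113: 42 days earlier.

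Later dating is more common, but it is not universal.

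**4. Average size.** Assumptions, none of them in the documents: exponential time to radiologic progression with median 35 to 120 days; a hold in 10%, 20% or 30% of cycles; hold length L uniform on 7 to 21 days; no clinical progression or death between scans. Cycle-tied scans were compared with scans fixed every 56 days, in 200,000 simulated patients per scenario.

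- *The whole hold falls on the cycle start.* Mean delay per hold = (7 + 21)/2 = 14 days. Mean dating is later by 1.9 to 6.4 days, and 3% to 25% of patients are dated earlier.
- *The hold begins at a random point in the 28-day cycle.* Only the overrun past the cycle end matters. Its mean for a given L is L²/(2 × 28). E[L²] = (21³ − 7³)/(3 × 14) = 8918/42 = 212.3, so the mean delay per hold is 212.3/56 = 3.8 days, about 27% of 14. Mean dating is later by 0.5 to 1.7 days, and 1% to 11% of patients are dated earlier.

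**5. The median.** Recorded dates cluster on scan days, so the median jumps. With the whole hold on the cycle start (fixed versus cycle-tied, days from first dose):

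- true median 35 days, 10% of cycles: 56 versus 56
- true median 45 days, 20%: 56 versus 72
- true median 60 days, 20%: 112 versus 88
- true median 90 days, 30%: 112 versus 127

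**The case against.** The strongest reply is that the effect is small and that many holds never reach the scan schedule.

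- **Not every hold moves a scan.** Omissions within a cycle, and abemaciclib-only holds while LY3214996 continues, need not delay a cycle start. The lengthening sentence stands in a paragraph about logistical delays, and no section says outright how a toxicity hold affects the cycle count. This stands, and it limits the scope. It does not remove the point: the rule on when a cycle begins is general, and no text keeps imaging on a calendar when a hold runs past the due date.
- **The shift is small beside sampling error.** With 28 patients and exponential PFS, the standard error of the Kaplan–Meier median is about m/(√28 × ln 2): 60/3.67 = 16 days to 120/3.67 = 33 days for medians of 60 to 120 days. The average shift also lies within the ±7-day visit window. This stands too, although a shift tied to tolerability does not average out as random error does.
- **Clinical progression and death do not wait for a scan.** Both count as PFS events, so the figures above overstate the effect on PFS.

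Some stronger readings are tempting, but the documents do not support them. A reader might infer that every patient with a hold is dated later, or that median PFS is inflated; steps 3 and 5 show otherwise. A reader might take a day-99 first scan as typical; it needs two full 21-day delays, each falling wholly on a cycle start. A reader might quote the proportion recorded progression-free after day 168, but that day is itself a scheduled scan date. With a 90-day median and 30% delays on the cycle start, fixed versus cycle-tied is 27.2% versus 35.6% after day 168, 42.2% versus 37.4% after day 167, and 27.2% versus 28.5% after day 196. The gain comes from the choice of landmark. Finally, the documents give neither Grade 2 event rates nor hold frequencies, so no figure here is a forecast for this trial.

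**Conclusion.** The point holds in limited form. Scans are tied to odd cycles, a late cycle start moves all later scans by the same number of days, and nothing in the documents offsets this. The first scan moves from day 57 to day 78 at most for one full 21-day delay of a cycle start.

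On average, radiologic progression is dated about 0.5 to 2 days later if holds start at random points in the cycle, and about 2 to 6 days later if each whole hold falls on the cycle start. Both ranges rest on assumed holds of 7 to 21 days in 10–30% of cycles and on exponential progression times.

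Secondary PFS and DOR therefore depend partly on dose delay. For DOR the direction is open, because both its start and its end are read from scans. With one arm there is no between-arm bias, and the ORR test and sample size stand. This is a cheap improvement, not a defect that threatens the trial's conclusion.

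**What to change.** Amend footnote E of Table 2.1 and Section 10.1 so that tumor assessments are done every 8 weeks (±7 days) counted from cycle 1 day 1, regardless of dose holds, cycle delays or cycle number, while the patient remains on study treatment. Eight weeks is the interval already intended (2 × 28 = 56 days). No dose or hold rule changes.

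The limit to patients on treatment is deliberate. Imaging until progression would add scans after treatment stops, whereas Section 9.4 ends follow-up at the 30-day safety visit.

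The cost is a wording change and about the same number of scans. The downside is that, in patients with delays, some scans will not fall on a cycle Day 1 visit. The change should be made prospectively, since the timing of a late scan cannot be recovered afterwards.

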3.1 Study Rationale

3.1.1 Rationale for Investigation of LY3214996, an ERK1/2 Inhibitor

The mitogen-activated protein kinase (MAPK) pathway is a key regulator of cellular proliferation and survival. Abnormalities of the MAPK pathway including alterations in BRAF, RAS, Neurofibromin-1 (NF1), and MEK are common in many cancers including melanoma, colorectal cancer (CRC), non-small cell lung cancer (NSCLC), pancreatic ductal adenocarcinoma (PDAC), ovarian cancer, and many others. Extracellular signal regulated kinase (ERK) is a downstream member of this pathway and plays a central role in transmitting extracellular signals from activated receptor tyrosine kinases (RTKs) such as epidermal growth factor receptor (EGFR), FGFR, PDGFR, VEGFR, and others. When activated, ERK1/2 phosphorylates RSK1, and regulates several additional downstream cytoplasmic and nuclear targets involved in cell cycle, cell proliferation, cell growth, and cell survival.

The feasibility of pharmacologic inhibition of the MAPK pathway in cancer has been shown through the success of BRAF and MEK inhibitors in the treatment of various cancer subtypes especially patients who harbor *BRAF* mutations. Two BRAF kinase inhibitors, vemurafenib and dabrafenib, are approved in the United States (US), Australia and several European countries for the treatment of melanoma patients with *BRAF*^{V600E} mutation. Two MEK kinase inhibitors – trametinib alone, and in combination with a BRAF inhibitor, dabrafenib, and cobimetinib, in combination with a BRAF inhibitor, vemurafenib – are approved by the Food and Drug Administration (FDA) for the treatment of unresectable or metastatic melanoma patients with *BRAF*^{V600E/K} mutations that have not received previous treatment with a BRAF inhibitor. However, while BRAF and MEK inhibitors have proven effective in these patient populations, most patients eventually develop drug resistance, which leads to disease relapse (Samatar et al. 2014). Most resistance mechanisms to RAF and MEK inhibitors result in reactivation of ERK1/2; therefore, blockade of ERK1/2 directly is postulated to overcome many of the current limitations of RAF and MEK inhibitors. In addition, RAF and MEK inhibitors remain ineffective in RAS-mutant cancers. Neurofibromin-1, a tumor suppressor gene, is a negative regulator of RAS. Loss of function of NF1 has been linked to the development of tumors in mice (Jacks et al. 1994). Neurofibromin-1 deletions and mutations are common in cancers and may recapitulate RAS mutations and represent an attractive target in the MAPK pathway (Jacks et al. 1994; Yap et al. 2014). LY3214996 is a potent inhibitor of ERK1/2 kinases that can potentially obviate resistance mechanisms in cancers that harbor BRAF, RAS, NF1, MEK, and other MAPK alterations. A general introduction of LY3214996 is provided in Section 3.2.1. Detailed information about LY3214996 is provided in the Investigator’s Brochure (IB).

3.1.2 Rationale for Combination Therapy

Activating mutations in *BRAF* and *KRAS*, key signaling components of the MAPK pathway, are among the most common oncogenic mutations in human cancers, occurring in ~7% and ~20% of all cancers. The frequency in common cancer histologies such as NSCLC, PDAC, CRC and melanoma (Oikonomou et al. 2014.). Genome and transcriptome wide analysis in various cancers demonstrated a diversity of altered pathway targets and feedback mechanisms that

contribute to disease pathogenesis and resistance. In MAPK driven cancers, this may explain the lack of success in *RAS* mutant tumors, limited efficacy of cancer agents in many *BRAF* mutant tumors and toxicities experienced by patients due to paradoxical signaling when these agents are given as a single agent. The feasibility and usefulness of combining agents that affect targets within the MAPK pathway has been clearly demonstrated by the success of combining BRAF and MEK inhibitors (vemurafenib and cobimetinib or dabrafenib with trametinib) in *BRAF*^{V600E/K} mutant melanoma patients, improving not just response rates and duration of response but in reducing the rates of certain therapy related toxicities. This underscores the importance of combination therapy in MAPK driven tumors.

3.1.2.1 Rationale for Exploring Combination Therapy with Abemaciclib in Tumors with Gain-of-Function Alterations in BRAF, RAF1, MEK1/2, and ERK1/2

3.1.2.1.1 *Abemaciclib Background/Rationale*

Abemaciclib is an orally bioavailable selective cyclin-dependent kinase (CDK) 4 and 6 inhibitor currently FDA approved as monotherapy and in combination with endocrine therapy in hormone-receptor positive breast cancer. It causes cell cycle arrest in Rb-proficient cells and has significant in vivo antitumor activity in several human cancer xenograft models (Spring et al. 2016). Abemaciclib crosses the blood brain barrier and has been shown to inhibit the growth of intracranial tumors both as a single agent and in combination with temozolomide (Raub et al. 2015). In a *KRAS*^{G12V} mouse model, a synthetic lethal interaction between the *KRAS*^{G12V} mutation and ablation of CDK4 was observed (Puyol M et al. 2010). Ablation of CDK4 leads to immediate senescence response in the lung tumors of *KRAS*^{G12V} animals. Increased sensitivity to abemaciclib has been observed preclinically both in in vitro and in vivo models of *KRAS* mutant NSCLC.

Abemaciclib has been or is currently being investigated in clinical trials

- Phase 1 study of abemaciclib for advanced NSCLC, breast cancer, and other solid tumors
- Phase 1 study of abemaciclib for Japanese patients with advanced cancer
- Phase 1b study of abemaciclib in combination with endocrine or targeted therapies for patients with advanced breast cancer
- Phase 1b study of abemaciclib in combination with another anti-cancer drugs for patients with NSCLC
- Phase 2 study of abemaciclib in relapsed or refractory mantle cell lymphoma
- Phase 2 Study of abemaciclib for patients with previously treated hormone receptor positive (HR+), HER2 negative metastatic breast cancer
- Phase 2 study for patients with brain metastasis secondary to HR+ breast cancer, NSCLC, or melanoma
- Phase 2 neoadjuvant study of abemaciclib for postmenopausal women with HR+, HER2 negative breast cancer (neoMONARCH)
- Phase 2 study of abemaciclib versus docetaxel for patients with stage intravenous (IV) squamous NSCLC previously treated with platinum-based chemotherapy
- Phase 3 study of fulvestrant with or without abemaciclib for patients with HR+, HER2 negative locally advanced or metastatic breast cancer (MONARCH 2)
- Phase 3 study of nonsteroidal aromatase inhibitors with or without abemaciclib in patients with HR+, HER2 negative locally advanced or metastatic breast cancer (MONARCH 3)

- Phase 3 study of abemaciclib plus best supportive care (BSC) versus erlotinib plus BSC for patients with stage IV NSCLC with a detectable KRAS mutation who have progressed after platinum-based chemotherapy (JUNIPER)

The safety profile of abemaciclib has been manageable when given as monotherapy or in the combinations investigated to date.

The Phase 2 MONARCH 1 study treated patients with endocrine resistant, hormone-receptor positive breast cancer with single-agent abemaciclib dosed at 200mg twice a day (N=132). Safety data from this study showed the most common treatment-emergent adverse events (TEAEs) ($\geq 20\%$) that occurred in patients included diarrhea (90.2%), fatigue (65.2%), nausea (64.4%), decreased appetite (45.5%), abdominal pain (38.6%), vomiting (34.8%), neutropenia (37.1%), anemia (25.0%), headache (20.5%) and thrombocytopenia (20.5%) (IB; Lilly 2019). More information about the known and expected benefits, risks and reasonably anticipated adverse events (AEs) may be found in the abemaciclib IB (IB; Lilly 2019).

3.1.2.1.2 **Rationale for Exploring Combination Therapy with Abemaciclib**

The importance of combination therapy to target various aspects of cancer pathogenesis has become more evident in an attempt to facilitate anti-tumor activity or to overcome acquired resistance in cancer. The RAF/MEK/ERK pathway is commonly mutated in a variety of solid tumors. While mutations in *BRAF* are the most common, particularly codon 600, a variety of additional mutations in the pathway have been identified that lead to pathway activation. Many of these mutations are uncommon but may lead to sensitivity to ERK inhibition. A recently published example of a patient with gallbladder cancer that harbored a rare gain-of-function *BRAF* L485W achieved a complete response with the ERK inhibitor, Ulixertinib (Sullivan et al. Cancer Discovery 2018). Unpublished preclinical data from Eli Lilly has demonstrated that gain-of-function mutations in MEK1/2 rendered cell lines sensitive to ERK inhibition. Open questions include ERK inhibitor sensitivity to other classes of mutations including *BRAF* fusions and *RAF1* amplification. Further, it is not known whether ERK inhibition may play a role in patients with *BRAF* mutations who have become resistant to BRAF inhibition.

Mitogens that stimulate the RAS-MAPK pathway are known to induce expression of D-type cyclins via the activation of downstream transcription factors in the AP1 or ETS family, which in turn activate CDK4 and CDK6, promoting cell cycle progression (Sherr 1996; Klein and Assoian 2008). Therefore, concomitant inhibition of the MAPK pathway exemplified by ERK inhibitors may augment the antitumor activity of CDK4 and 6 inhibitors like abemaciclib. Previous published data has also demonstrated that CDK4/6 inhibition is synergistic with inhibition of the MEK/ERK pathway (de Leeuw et al. Clin Can Res. 2018, Hart LS et al. Clin Can Res. 2016). To this end, Lilly has an ongoing phase I trial combining LY3214996 with Abemaciclib (CDK4/6 inhibitor) for which an RP2D of the combination is established at LY3214996 200 mg orally daily with abemaciclib 150 mg orally twice daily.

The manageable clinical safety profile of abemaciclib and preclinical safety data for LY3214996, coupled with the additive effects of the combination pre-clinical data provide the rationale for clinically evaluating the combination of LY3214996 and abemaciclib in the clinical setting in

tumors with overactivated MAPK pathway identified via pathogenic alterations in *BRAF*, *RAF1*, *MEK1/2*, *ERK1/2*, and *NF1*.

Expected overlapping toxicities of the combination include nausea, vomiting, fatigue, diarrhea, decreased appetite, blood creatinine increase, and alanine aminotransferase increased. Though rash is not considered an overlapping toxicity, an increased incidence of maculo-papular rash and dermatitis acneiform was observed in the combination during dose escalation of the phase 1 JUAB study.

